6. ASSESSMENT AND FOLLOW-UP

Patients will be followed up at 6-8 weeks after surgery in clinic as normal practice and will be asked to fill in a quality of life questionnaire at this time.

It is normal practice for patients to be followed up at one year after surgery with a repeat transthoracic echocardiogram prior to this appointment. Before this appointment, they will have an additional repeat cardiac MRI, CPET, pulmonary function tests and quality of life questionnaire at 6-9 months after surgery.

7. STATISTICS AND DATA ANALYSIS

The myocardial specimens will be preserved in formalin and transferred to the pathology laboratory at Hammersmith Hospital for processing and histological analysis. Spare sections will be fixed in Polysine slides and stored in the pathology laboratory at Hammersmith Hospital.

All data will be expressed as mean with standard error. Statistical comparison will be performed by one-way ANOVA followed by unpaired t-test as appropriate. Results will be considered statistically significant if P<0.05.

Data and all appropriate documentation will be stored for a minimum of 10 years after the completion of the study at Imperial College.

8. **REGULATORY ISSUES**

8.1 ETHICS APPROVAL

The Chief Investigator has obtained approval from the xxx Research Ethics Committee and the HRA. The study will be conducted in accordance with the recommendations for physicians involved in research on human subjects adopted by the 18th World Medical Assembly, Helsinki 1964 and later revisions.

[name] 22/12/16 16:42 Deleted: 2 [name] 22/12/16 16:43 Deleted: 1 [name] 22/12/16 16:43 Deleted: 9

8.2 CONSENT

Consent to enter the study must be sought from each participant only after a full explanation has been given, an information leaflet offered and time allowed for consideration. Signed participant consent should be obtained. The right of the participant to refuse to participate without giving reasons must be respected. After the participant has entered the study the clinician remains free to give alternative treatment to that specified in the protocol at any stage if he/she feels it is in the participant's best interest, but the reasons for doing so should be recorded. In these cases the participants remain within the study for the purposes of follow-up and data analysis. All participants are free to withdraw at any time from the protocol treatment without giving reasons and without prejudicing further treatment.

8.3 CONFIDENTIALITY

The Chief Investigator will preserve the confidentiality of participants taking part in the study and is registered under the Data Protection Act. All patients will be anonymised by assigning a study number. The code to this and study data will be kept on Imperial College NHS Trust computers. Only anonymised data will be analysed by the statisticians at Imperial College, London.

8.4 INDEMNITY

Imperial College, London holds negligent harm and non-negligent harm insurance policies which apply to this study.

8.5 SPONSOR

Imperial College, London will act as the main Sponsor for this study. Delegated responsibilities will be assigned to the NHS trusts taking part in this study.

8.6 FUNDING

This study is pending funding applications to Heart Research UK, Rosetrees Trust and British Heart Foundation.

8.7 AUDITS

The study may be subject to inspection and audit by Imperial College London under their remit as sponsor and other regulatory bodies to ensure adherence to GCP and the NHS Research Governance Framework for Health and Social Care (2nd edition).

9. STUDY MANAGEMENT

The day-to-day management of the study will be co-ordinated through [name] and [name], Department of Cardiothoracic Surgery, Hammersmith Hospital.

10. PUBLICATION POLICY

Study data will be disseminated through academic presentations and publications.

RIPCOM 1

The right ventricular pulmonary circulation in mitral valve disease study 1

Statistical methods

Version 1 31/12/2016 IRAS ID 199676

MAIN SPONSOR: Imperial College London FUNDERS: Applications to Heart Research UK, Rosetrees Trust and British Heart Foundation pending STUDY COORDINATION CENTRE: Department of Cardiothoracic Surgery, Hammersmith Hospital NRES reference: 199676

Protocol authorised by:

Name & Role	Date	Signature
[name]	31/12/16	
[name]	31/12/16	
[name]	31/12/16	

Statistical methods

Data are presented as mean \pm SD for continuous numerical variables and as count and percentages for categorical variables. Normality was assessed with Lilliefors (Kolmogorov-Smirnov) normality test: for consistency in reporting the data we have reported the numerical variables as mean \pm SD regardless their distribution. We compared the pre-operative characteristics, echocardiographic characteristics and CPET variables between class 1 and class 2 diagnosis with Student t-test for normally distributed numerical variables and Mann-Whitney (Wilcoxon) test for not normally distributed numerical variables. The comparison between categorical variables was conducted with Chi-square test or Fisher Exact test as appropriate. The CPET results before and after surgery have been compared using paired t-test or paired Wilcoxon test depending on the distribution.

Primary Outcome: reduced functional capacity at follow up

This was a per protocol analysis. To identify the predictors of reduced functional capacity we have run two different types of regression models. In the first model (linear regression) we have treated our outcome (VO2 % at follow up) as a numerical continuous variable. The predictors were evaluated trough a univariable analysis first and then a multiple model was run including those predictors that appeared to be significant at univariable analysis. The final model was obtained via a backward selection using AIC (Aikake Information Criterion) as criterion.

In the second model, the outcome was defined as a dichotomic variable that included a VO2% of $\leq 84\%$ and/or LVEF $\leq 50\%$ at follow up. To evaluate the predictors of

this outcome we have run univariable and multivariable logistic regression model. In consideration of the fact that the overall number of events for this outcome was limited, the final multiple model was a parsimonious model developed using a meaningful selection of the variables that were considered relevant in previous published research (preoperative LVEF \leq 60 %, LVESD \geq 40 mm and ppVO2 % $\leq 84\%$) plus the class of surgical indication.

Correlation between TTE parameters and MRI parameters

Linear models have been run to compare some TTE parameters with the same MRI models.

Comparing changes in quality of life between class of indication of surgery Linear mixed effects models were fitted for longitudinal (repeated measures) outcomes (physical functioning and social functioning) adjusted for time, preoperative percentage predicted peak VO2, preoperative LVEDD and preoperative LVESD.

For each of the main outcomes a stepwise approach has been used to model the data: first, an unconditional means model was run to describe the data and to test the null hypothesis; then an Unconditional Growth Model to set up the slope has been run followed by a Conditional Growth model (to set up the intercept). The unconditional mean model determines if the intercept is different from zero and if there is subjectrelated variability. The unconditional growth model can have a fixed or a random slope: the fixed slope is based on the assumption that each individual in the dataset is following a similar pattern over time, while the random slope allows individual variability. Both models have been run to find out the best fitting model. The Conditional growth model is the final step and it is the complete final model adjusted for the covariates. All models were fitted using maximum likelihood methods.

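### The class 1 versus class 2 comparisons default to a Student t-test with no provision for unequal variances, so the 5% error rate is not kept if the classes differ in both size and SD

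*SAP*

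**What the plan says.** The SAP's opening paragraph sets out the two-group comparisons: "We compared the pre-operative characteristics, echocardiographic characteristics and CPET variables between class 1 and class 2 diagnosis". The test for continuous variables is chosen "with Student t-test for normally distributed numerical variables and Mann-Whitney (Wilcoxon) test for not normally distributed numerical variables", and the choice rests on one check: "Normality was assessed with Lilliefors (Kolmogorov-Smirnov) normality test". The SAP does not give the level of that check or say whether it is run within each class or on pooled data. It does not mention equality of variances or a Welch correction, and it does not give the class sizes.

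Protocol section 7 is shorter: "Statistical comparison will be performed by one-way ANOVA followed by unpaired t-test as appropriate". It adds the only stated threshold: "Results will be considered statistically significant if P<0.05". It sets no condition on variances either. Protocol section 3 describes three strata, defined by symptoms and by ejection fraction around 60%. The Study Summary gives a population of 50.

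**The concern.** In its usual meaning the Student t-test pools the two variances, which assumes that they are equal. A normality check cannot test that assumption, because two perfectly normal groups may have very different SDs.

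The groups here are not randomised. They are formed by clinical status, so one may be much smaller than the other. Spread may differ too: a stratum cut at an ejection-fraction threshold is bounded on one side, so unequal spread in ventricular function and related measures is plausible. The documents neither show it nor rule it out.

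At stake are the P values for every continuous class comparison that goes through this rule, CPET variables included. They could be too small or too large, depending on whether the smaller class is the more or the less variable. The plan gives no means of knowing which.

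**Working it through.** **Inputs**
- Total of 50 patients (Protocol, Study Summary).
- Threshold 0.05 (Protocol section 7). Two-sided is assumed, as no side is stated.
- Test rule as in the SAP, with Lilliefors assumed to be run at 5% within each class.
- Class sizes and SDs are not in the documents. Assumed splits run from 25/25 to 8/42. The assumed ratio r, smaller-class SD over larger-class SD, is mainly 2 or 0.5.

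**Step 1. Reproduce the nominal 5%.** With normal data and r = 1, simulation (20,000 replicates per split) gives 4.9% to 5.2% for the Student t-test at every split, 8/42 included. Imbalance alone does no harm.

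**Step 2. Hand approximation with unequal SDs.** Set the larger-class SD to 1.
- True variance of the mean difference: V = r²/n₁ + 1/n₂.
- Variance the pooled test uses on average: W = s²(1/n₁ + 1/n₂), with s² = [(n₁ − 1)r² + (n₂ − 1)]/48.
- With k = V/W, the error rate is about P(|T₄₈| > 2.011/√k).

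For 12/38 and r = 2:
- V = 4/12 + 1/38 = 0.3596
- s² = (11×4 + 37)/48 = 1.6875
- W = 1.6875 × 0.10965 = 0.1850
- k = 1.944 and 2.011/√1.944 = 1.442, giving about 15.6%.

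For 12/38 and r = 0.5:
- V = 0.25/12 + 1/38 = 0.0472
- s² = (11×0.25 + 37)/48 = 0.8281
- W = 0.0908
- k = 0.519 and 2.011/√0.519 = 2.79, giving about 0.8%.

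For 25/25, V = (r² + 1)/25 and W = [(r² + 1)/2] × (2/25), so k = 1 whatever r is.

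**Step 3. Simulation (normal data, 20,000 replicates).**

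| Split | r | k | Hand | Student | SAP rule | Welch |
|---|---|---|---|---|---|---|
| 20/30 | 2 | 1.28 | 8.2% | 8.2% | 8.3% | 4.8% |
| 15/35 | 2 | 1.65 | 12.4% | 12.8% | 12.7% | 4.9% |
| 12/38 | 2 | 1.94 | 15.6% | 15.5% | 15.2% | 5.0% |
| 8/42 | 2 | 2.45 | 20.5% | 20.7% | 20.2% | 4.9% |
| 20/30 | 0.5 | 0.78 | 2.8% | 2.7% | 2.9% | 4.7% |
| 15/35 | 0.5 | 0.61 | 1.3% | 1.3% | 1.5% | 5.2% |
| 12/38 | 0.5 | 0.52 | 0.8% | 0.8% | 1.1% | 5.1% |
| 8/42 | 0.5 | 0.42 | 0.3% | 0.4% | 0.5% | 5.1% |

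Longer runs of the Student t-test at r = 2 gave 8.4% at 20/30, 12.7% at 15/35 and 15.9% at 12/38. At r = 1.2 it is about 6% at 20/30 and 7% at 12/38.

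**Step 4. What the gate does.** With normal data about 90% of samples pass Lilliefors in both classes whatever r is, so the rule's error rate stays close to that of the plain Student t-test. The gate neither causes the departure nor catches it. Mann-Whitney is not a safe fallback for unequal spread: at 10/40 it gives 10.4% (r = 2) or 1.4% (r = 0.5). Under skew it also answers a different question. With equal means, lognormal data (log-SD 0.5), 25/25 and r = 2, the rule rejects in 11.7% of samples and the Student t-test in 5.7%, because Mann-Whitney does not test means.

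**Step 5. Three strata.** Ordinary one-way ANOVA behaves in the same way. With assumed strata of 8, 17 and 25 and the smallest stratum's SD doubled, it rejects in about 15% of samples; Welch ANOVA rejects in about 5%.

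**Step 6. Price of Welch.** With normal data, equal SDs and a standardised difference of 0.8 to 1.0, power against the Student t-test falls by under 1 point at 20/30, about 3 points at 12/38 and 6 to 8 points at 8/42. With skewed data and a very small class, Welch runs above 5%: up to 7.6% at 10/40.

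**The case against.** The strongest reply is that the documents give no class sizes, no SDs and no reason to expect a twofold ratio. That stands: the figures are conditional, and moderate cases are mild. A second reply is that these are unadjusted comparisons of patient characteristics. That also stands. The SAP's primary outcome uses linear and logistic regression, quality of life uses mixed models, and CPET before and after surgery is compared with paired tests. A third is that the protocol's "one-way ANOVA followed by unpaired t-test as appropriate" has no normality gate, does not say Student and does not exclude Welch. For the t-test that is fair, so the protocol point is one of specification. One-way ANOVA named without qualification does, however, normally mean the equal-variance form.

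A reader might go further in four ways, none of which the documents support:
- **That small, unequal groups are enough to break the test.** They are not. With equal SDs the rate is about 5% even at 8/42.
- **That the Lilliefors pre-test inflates the error.** With normal data the rule and the plain Student t-test agree closely. The cause is the pooled variance.
- **That a false-positive rate of 15 to 20% is to be expected, or that the P values are wrong.** That range needs a split of about 12/38 or worse together with about a twofold SD ratio in the adverse direction.
- **That the primary result is undermined.** It does not depend on this two-sample test.

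**Conclusion.** The point holds as a conditional weakness of modest weight. The SAP's default test assumes equal variances, nothing in the plan checks or justifies this, and the groups are of a kind where it cannot be taken for granted. If the classes differ in both size and SD, an SD ratio of 2 moves the nominal 5% to about 8%, 12 to 13% or 16% at 20/30, 15/35 or 12/38 when the smaller class is more variable, and to about 3%, 1% or 1% when it is less variable. Welch holds about 5% in all of these.

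This rests on assumed splits of 50, assumed SD ratios, normal data, a two-sided 5% level and the usual meaning of the Student t-test. If either the sizes or the SDs prove close to equal, the practical effect is small. It is worth changing because a better method can be named in a sentence, not because the error is known to be large.

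**What to change.** Replace the SAP's test-selection sentence with wording such as: Continuous variables will be compared between class 1 and class 2 with the Welch (unequal-variance) t-test at the two-sided 5% level. For each variable we will give the number of patients and SD in each class and the mean difference with its 95% CI. A Mann-Whitney test will be reported as a sensitivity result. Normality will be described but will not determine the test.

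If the three protocol strata are compared, name Welch ANOVA followed by Welch t-tests in place of ordinary ANOVA and an unspecified unpaired t-test, in both documents. The sponsor should confirm that two-sided testing is intended.

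No data-dependent transformation rule should be added: it would bring back a choice of method made after seeing the data, and on the log scale it would no longer estimate a mean difference.

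The work is a short text change and a software option. The statistical cost is the power loss shown in Step 6, which is negligible for nearly balanced classes but real if one class has about 8 patients. With skewed data and a very small class, Welch is only approximate, which is the reason for keeping the Mann-Whitney result alongside it.

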1.2 RATIONALE FOR CURRENT STUDY

To identify objective markers of exercise capacity, cardiac or respiratory function that will demonstrate the earliest point at which patients with severe mitral valve disease derive prognostic benefit from surgery.

Patients with severe mitral valve disease and symptoms although gaining benefit from surgery have a worse long term prognosis and quality of life than the general population. There is currently no proven prognostic benefit for surgery on asymptomatic patients. Therefore there will be an objective point between the two ends of the disease spectrum at which patients will derive early prognostic benefit and enable a return to a normal life expectancy and quality of life.

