Quality of life questionnaire- At the preassessment clinic, patients will be asked to fill out a validated quality of life questionnaire (SF-36 health survey).

Intra-operative specimens

Heart muscle biopsies will be obtained at the time of clinically indicated heart surgery. Two small heart samples approximately 0.8 grams each or the size of a cooked rice grain will be taken from the left and right ventricle. The specimens will be preserved in formalin and processed and analysed at the Department of Pathology by a pathologist with a specialist interest in cardiac pathology. The samples will be fixed and analysed with haematoxylin and eosin for structure, Elastin van Gieson stain for elastin, Martius, Scarlet and Blue stain for fibrin, Picrosirius red stain for collagen, Perls' Prussian blue stain for iron, Periodic acid-Schiff stain for polysaccharides, Desmin stain for smooth muscle, CD68 for monocytes, CD45 for leucocytes, smooth muscle actin for smooth muscle and CD31 for vascular endothelium.

[name] 22/12/16 16:42 Deleted: 2 [name] 22/12/16 16:43 Deleted: 1 [name] 22/12/16 16:43 Deleted: 9

By correlating the results of the histological analysis with clinical markers such as left and right ventricle function and pulmonary hypertension, and the cardiac imaging on transthoracic echocardiogram and cardiac MRI this will enable us to grade microscopic changes in the myocardium throughout the spectrum of mitral valve disease from asymptomatic to symptomatic.

In addition, the results of the histological analysis will be the basis of further collaborative work with the Myocardial Function group at the Imperial Centre for Translational and Experimental Medicine.

Post-operative follow up

6-8 weeks- it is normal practice for patients to be reviewed at 6-8 weeks after surgery in clinic with clinical history and examination. Patients will be asked to fill in a quality of life questionnaire at this time.

6-9 months- Patients will have a repeat transthoracic echocardiogram, cardiac MRI, CPET, pulmonary function tests. A quality of life questionnaire will be mailed to patients with a self-addressed envelope.

12 months- it is normal practice for patients to be followed up at 12 months after surgery with clinical history and examination.

Review of investigations

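### The first primary model does not guarantee adjustment for pre-operative VO2%: predictors are screened unadjusted, and no rule holds that baseline in the multiple model

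*SAP*

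**What the plan says.** The SAP's section on the primary outcome takes VO2% at follow-up as a continuous variable in a linear regression. Predictors are first tested singly; "then a multiple model was run including those predictors that appeared to be significant at univariable analysis". Then "The final model was obtained via a backward selection using AIC". The text lists no candidates, gives no significance threshold for the screen and protects no variable from removal.

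Pre-operative VO2% is available. The schedule in Protocol Appendix 1 has CPET before surgery and at 6-9 months. Protocol section 3 says of the later visit: "Patients will have a repeat transthoracic echocardiogram, cardiac MRI, CPET, pulmonary function tests". The SAP also uses the two tests as a pair: "The CPET results before and after surgery have been compared using paired t-test" (or its rank equivalent).

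Elsewhere the SAP names this baseline. In the logistic model "the final multiple model was a parsimonious model developed using a meaningful selection of the variables", and pre-operative percentage predicted VO2, cut at 84%, is one of those variables. The quality-of-life models are "adjusted for time, preoperative percentage predicted peak VO2, preoperative LVEDD and preoperative LVESD".

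**The concern.** Pre-operative VO2% is the baseline of this model's own outcome, yet the linear model is the one place where the SAP does not name it. Protocol section 1.2 gives the purpose: "To identify objective markers of exercise capacity, cardiac or respiratory function", so as to find the point at which surgery helps. Protocol section 3.1 lists pilot data on change in exercise capacity. For either use, a reader will want to know whether a marker says more than the CPET already done before surgery.

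Two things can go wrong:
- The unadjusted screen can discard a marker that adds to baseline before any adjustment takes place.
- If baseline is not a candidate, or is dropped, a marker with no information of its own can stay in the model because it mirrors pre-operative fitness.

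**Working it through.** The documents give no effect size, SD or power calculation, so there is no figure of the plan's to reproduce.

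**Inputs from the documents.** n = 50 (Protocol study summary). For the level, Protocol section 7 says "Results will be considered statistically significant if P<0.05". I take this as two-sided and apply it to the screen, for which the SAP gives no threshold.

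**Assumed inputs.** Baseline-to-follow-up correlation 0.6 (range 0.4 to 0.8); marker's standardised effect given baseline 0.3; 20 candidates; follow-up CPET in all 50 (40 and 30 also shown). VO2% is taken to be the same measure before and after surgery. The adjusted test is marker plus baseline at P<0.05.

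**Step 1. Marker uncorrelated with baseline (Fisher z).**
- Screen: r = 0.30; atanh(0.30) × √47 = 0.3095 × 6.856 = 2.12. Missed: Φ(1.96 − 2.12) = 44%.
- Adjusted: partial r = 0.3/√(1 − 0.36) = 0.375; atanh(0.375) × √46 = 0.3942 × 6.782 = 2.67. Missed: Φ(1.96 − 2.67) = 24%.
- Equivalent size: 4 + (2.12/0.3942)² ≈ 33. The screen in 50 patients has the power of an adjusted test in about 33 (43 if the baseline correlation is 0.4; 19 if it is 0.8).
- With 40 patients the misses are 53% v 34%; with 30, 64% v 48%.

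**Step 2. Full procedure by simulation** (screen, multiple model, backward AIC; baseline a candidate; ranges cover three scalings of the outcome variance and repeat runs).

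| Marker-baseline correlation | Missed, SAP rule | Missed, adjusted test |
|---|---|---|
| −0.2 | 75-79% | 25-31% |
| 0 | 43-48% | 22-30% |
| +0.2 | 17-26% | 24-33% |
| +0.4 | 15-21% | 29-37% |

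The sign decides the direction. When a marker's correlation with baseline shares the sign of its effect, the SAP rule misses fewer. At equal false-kept rates that advantage shrinks but remains (19% v 23% at +0.2; 16% v 24% at +0.4).

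**Step 3. Screen threshold, correlation 0.** Screens at 0.05, 0.10 and 0.20 miss about 44%, 32% and 21-23%, so at 0.20 the gap to the adjusted test closes. But they keep 3.5%, 5.7% and 9.4% of inert markers. With the adjusted test set to the same false-kept rate, misses are 43% v 27%, 32% v 20% and 21% v 14%.

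**Step 4. Inert marker correlated 0.4 with baseline.** Its unadjusted correlation with the outcome is 0.4 × 0.6 = 0.24. Then atanh(0.24) × √47 = 0.2448 × 6.856 = 1.68, and it passes the screen with probability Φ(1.68 − 1.96) = 39%. In the full procedure it is kept in 23-39% of runs if baseline is not a candidate (14-17% at baseline correlation 0.4). If baseline is a candidate it is kept in 8-11%. The adjusted test flags it in about 5%.

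**Step 5. Does baseline survive when it is a candidate?** At n = 50 it is in the final model in over 99% of runs at correlation 0.6, and in about 68-84% at 0.4. In a separate simulation with one marker and baseline as the only candidates, it stays in 50-58% at correlation 0.3 with n = 50, and in 32-58% over n = 30 to 50.

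**Step 6. Is holding baseline in enough?** No. With the unadjusted screen kept, about 43-44% of uncorrelated markers are still missed. If baseline was not a candidate, holding it in cuts retention of the inert marker from 38% to about 8-9%. Each change repairs a different fault.

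**Step 7. Size of reported effects.** When the real marker is kept by the SAP rule, its mean estimate (true value 0.30) is 0.35 at correlation 0 and 0.38-0.40 at −0.2. The adjusted estimate, always reported, averages 0.30 with 95% coverage.

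**The case against.** A reader might infer that this model can show only which markers track follow-up fitness, never which add to pre-operative fitness. The documents do not support that. The final model is a multiple model, and without a candidate list baseline is neither included nor excluded. If it is a candidate and correlates 0.6 with the outcome, it nearly always survives (step 5), and the other coefficients are then adjusted for it.

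The SAP also states its aim as predictors of reduced capacity at follow-up, which is a status, not an increment over baseline. Added value is a reasonable question here, but the SAP does not state it as its question.

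Nor does the screen always lose power. The protocol's primary objective expects exercise capacity and cardiac function to be correlated, so shared signs are plausible, and there the SAP rule misses fewer markers.

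Finally, adjusting each marker for baseline alone would give up mutual adjustment. With an inert marker correlated 0.5-0.7 with a real one, the baseline-adjusted test flags it in 20-45% of runs, while the SAP procedure keeps it in 6-17%.

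These points stand, and they narrow the claim. They do not remove it: the plan contains no rule that secures adjustment, and a marker lost at the screen cannot be recovered by the later model.

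**Conclusion.** The point holds in this form: adjustment for pre-operative VO2% is not guaranteed in the first primary model. It should be fixed, because the baseline is already collected and the SAP names it in two other analyses.

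The size is conditional. With 50 patients, baseline correlation 0.6 and marker effect 0.3, the miss rate is about 44% v 24% for an uncorrelated marker. It is worse with opposing signs and reversed with shared signs. Retention of an inert marker reaches about 39% only if baseline is not a candidate. Apart from n = 50 and the 0.05 level, every input is assumed, and the number with follow-up CPET is not given. The gap is confined to the linear model.

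**What to change.** - Hold continuous pre-operative VO2% in every fit of the linear model, including the one-at-a-time step.
- Do not use the unadjusted p-value as the entry rule.
- List the candidates and state how many were examined. Report each marker's baseline-adjusted estimate with a 95% CI, whatever its p-value.
- Keep a multivariable model with baseline held in it, so that correlated markers are also adjusted for each other, and label it exploratory. If its terms are selected, give bootstrap optimism-corrected performance with every selection step repeated in each resample.
- If the models have already been run, declare this as a re-analysis.

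The cost is SAP text and a re-run on data the trial already collects. There are three downsides. Sensitivity falls for markers whose correlation with baseline shares the sign of their effect (at +0.4, 29-37% missed v 15-21%). Estimates adjusted for baseline alone can flag a marker that only stands in for another, so they should be read beside the multivariable model. Multiplicity across markers is disclosed, not removed.

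### The logistic model for reduced functional capacity counts a low LVEF alone as an event, and it cuts three continuous predictors at thresholds without need

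*SAP*

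**What the plan says.** The SAP section headed "Primary Outcome: reduced functional capacity at follow up" gives one purpose for two models: "To identify the predictors of reduced functional capacity we have run two different types of regression models".

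- **Linear model.** Here "we have treated our outcome (VO2 % at follow up) as a numerical continuous variable". LVEF plays no part in this outcome.
- **Logistic model.** Here "the outcome was defined as a dichotomic variable that included a VO2" percentage of at most 84, "and/or LVEF $\leq 50\%$ at follow up". Either component alone makes an event.

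The SAP says that events were few and that the final logistic model was therefore kept small. Its variables "were considered relevant in previous published research (preoperative LVEF" of at most 60%, LVESD of at least 40 mm and ppVO2 of at most 84%), "plus the class of surgical indication". No reason is given for entering the three measurements as indicators.

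The protocol keeps the two constructs apart. Section 2 makes the primary objective a correlation of exercise capacity on CPET with quality of life and with cardiac function on echocardiography and MRI. Section 3 describes CPET as the measure of exercise capacity and lists ejection fraction among the MRI parameters. The protocol defines no composite of the two.

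**The concern.** There are two separate problems, both in the logistic model.

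**Label.** The event mixes the two things that the protocol sets out to relate. Preoperative LVEF is a predictor, and follow-up LVEF is one way to become an event. If preoperative LVEF shows a raised odds ratio, the model cannot say whether it predicts poor exercise capacity or only later LVEF. The same ambiguity applies in mirror image to preoperative ppVO2 and the VO2% component. Protocol section 1.2 says that the study looks for objective markers bearing on the timing of surgery, so attributing a predictor to the wrong outcome would touch its main message.

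**Coding.** Few events are a good reason to use few variables. They are no reason to cut the ones chosen: one indicator and one linear term each use one degree of freedom, and the indicator carries less information. In a study of 50 patients (protocol, Study Summary) that loss matters.

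**Working it through.** The documents give no event count, component prevalence, predictor distribution or power, so there is no planned figure to reproduce. Everything below rests on stated assumptions.

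**1. Share of composite events that are LVEF-only**

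Let V be the proportion with follow-up VO2% ≤84, E the proportion with follow-up LVEF ≤50%, and B the proportion with both. B comes from a bivariate normal distribution with correlation r.

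Share = (E − B) / (V + E − B)

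| V | E | r | B | Share |
|---|---|---|---|---|
| 25% | 10% | 0 | 2.5% | 7.5/32.5 = 23% |
| 25% | 10% | 0.3 | 4.4% | 5.6/30.6 = 18% |
| 25% | 25% | 0 | 6.25% | 18.75/43.75 = 43% |
| 25% | 25% | 0.3 | 9.5% | 15.5/40.5 = 38% |
| 40% | 10% | 0 | 4.0% | 6.0/46.0 = 13% |
| 40% | 10% | 0.3 | 6.1% | 3.9/43.9 = 9% |
| 40% | 25% | 0 | 10.0% | 15.0/55.0 = 27% |
| 40% | 25% | 0.3 | 13.8% | 11.2/51.2 = 22% |

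The range is about 9% to 43%.

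**2. Can the LVEF component alone create an apparent predictor?**

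Suppose that preoperative LVEF and follow-up LVEF are both unrelated to follow-up VO2%. Assume that 40% have preoperative LVEF ≤60% and that preoperative and follow-up LVEF correlate at 0.4-0.6, with V and E as above. The composite risk in each group is 1 − (1 − V)(1 − e), where e is that group's risk of follow-up LVEF ≤50%.

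- Low end (correlation 0.4, E = 10%, V = 40%): e is 17.1% with low preoperative LVEF and 5.25% without. Composite risks are 1 − 0.60 × 0.829 = 50.3% and 1 − 0.60 × 0.9475 = 43.2%. The odds ratio is (0.503/0.497)/(0.432/0.568) = 1.3.
- High end (correlation 0.6, E = 25%, V = 25%): e is 45.2% and 11.5%. Composite risks are 1 − 0.75 × 0.548 = 58.9% and 1 − 0.75 × 0.885 = 33.6%. The odds ratio is (0.589/0.411)/(0.336/0.664) = 2.8.

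An unadjusted odds ratio of about 1.3 to 2.8 can thus arise with no relation to exercise capacity at all.

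**3. Information kept when a predictor is cut**

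For one normal predictor with a linear effect, cut so that a proportion p lies beyond the threshold c:

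Efficiency = φ(c)² / [p(1 − p)]

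- p = 0.50: 0.3989²/0.25 = 0.637, and 50 × 0.637 = 31.8 patients' worth
- p = 0.25: 0.3178²/0.1875 = 0.539, and 50 × 0.539 = 26.9
- p = 0.20: 0.2800²/0.16 = 0.490, and 50 × 0.490 = 24.5

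**4. Effect on power**

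This was simulated with one predictor, 50 patients, two-sided 5% and 1,500 samples per setting, for event rates of 30-50% and 30-50% of patients beyond the cut. At a latent correlation of 0.4, logistic power is about 39-48% with the predictor cut and 60-66% with it continuous. At 0.5 it is about 59-68% and 82-87%.

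**The case against.** **The SAP already has a model without the problem.** The linear model uses continuous VO2%, and a reader can set it beside the logistic result. This stands, and it limits the fault to the logistic model. It does not repair the label: both models are presented as identifying predictors of the same thing.

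**The thresholds answer a clinical question.** They are fixed in the text, the SAP links the variables to earlier research, and protocol section 3 stratifies at an ejection fraction of 60%. Whether patients beyond an established cut-off do worse is a fair question, and a different one from a per-unit slope. That justifies showing the cut-off version. It does not make it the better main model when events are few. Nor should the cut-offs be read as searched for in the data; nothing in the SAP suggests that.

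**One degree of freedom is enough only if the effect is linear on the logit scale.** This stands. Allowing for curvature would cost further terms.

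**Preoperative LVEF might be thought to predict the composite almost by construction.** The documents do not support that. The predictor threshold is 60%, the outcome threshold is 50%, and surgery and months of follow-up lie between. A baseline value predicting its own later value is ordinary prognosis. The fault is that the pooled odds ratio hides which component is being predicted.

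**A reader might also infer that the study as a whole loses the equivalent of 18 to 25 patients.** That goes too far. The efficiencies apply to one normal predictor with a linear effect, while the final logistic model has four predictors. Threshold coding is documented only for that final model; the coding in the linear and univariable models is not stated. The analysis is also per protocol, so the number analysed need not be 50.

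**Conclusion.** The point holds for the second model only. Its event definition does not match its label, and its pooled odds ratios cannot separate exercise capacity from later LVEF. About 9-43% of events would be LVEF-only if low VO2% occurs in 25-40%, low LVEF in 10-25%, and the two correlate at 0-0.3; none of these inputs is in the documents.

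Cutting the three predictors costs precision without saving model complexity. The 64%, 54% and 49% figures show the order of the loss per predictor under normality, linearity and assumed splits. They do not estimate the loss in this four-predictor model.

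The documents do not support the wider reading that the whole primary analysis is mislabelled, because the continuous VO2% model measures what its heading says. A composite of low VO2% or low LVEF is also a legitimate endpoint if it is named for what it contains. The change is worth making, but the study's analysis does not fall without it.

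**What to change.** 1. Enter preoperative LVEF, LVESD and ppVO2 as continuous linear terms in the main logistic model. Report the version with the published cut-offs as a supplementary analysis.
2. Keep continuous follow-up VO2% as the analysis labelled functional capacity.
3. Rename the composite, for example *reduced exercise capacity or LV dysfunction*, and make it secondary. Report VO2% ≤84 and LVEF ≤50% separately, with the number of events from each alone and from both.

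**Cost.** No new data are needed. The SAP wording changes, and because the SAP describes the models as already run, the logistic model must be refitted. Odds ratios in the main model become per unit rather than per published cut-off, and linearity on the logit scale is assumed and should be stated.
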